5.7.3.2 Main Secondary Analyses

5.7.3.2.1 CMAP Total Amplitude at Week 40

CMAP total amplitude at Week 40 will be analysed using the same MMRM model used for the primary analysis.

5.7.3.2.2 Incidence of Recovery of CMAP Total Amplitude at Week 28 and Week 40

Incidence of recovery of CMAP total amplitude at Weeks 28 and 40 will be analysed for each of the two timepoints by estimating proportion of participants with recovery in each of the treatment arms, p_D in the Dysport arm, p_B in the Botox arm, p_X in the Xeomin arm, as well as the risk differences $p_D - p_B$ and $p_D - p_X$ with point estimates as well as according exact

(Clopper-Pearson) 95% CI for p_D , p_B and p_X and exact unconditional 95% CI for the risk differences.

A Fisher's Exact Test (one-sided, significance level 2.5%) will be used for testing each of the comparisons of Dysport to Botox or Xeomin respectively in the framework of the multiple testing procedure described in [Section 5.7.1.3](#).

5.7.3.3 *Subgroup Analysis*

No subgroup analyses will be performed.

5.7.3.4 *Supplementary Analysis*

In case of occurrence of major PDs with the potential to interfere with CMAP total amplitude ([see section 5.3](#)), a supplementary analysis using the same models used for the main secondary analyses will be conducted using a treatment policy strategy to handle this ICE. All collected data will be taken into account in this supplementary analysis, even when occurring after PDs.

5.7.4 *Analysis of Other Secondary Pharmacodynamic Endpoints*

To further characterise the pharmacodynamic profile of a single intramuscular administration of study intervention at reducing the CMAP total amplitude of the stimulated EDB, the following secondary pharmacodynamic endpoints will be evaluated:

- Time to onset of action defined as first timepoint where EBD CMAP total amplitude is less or equal to 85% of the baseline value
- Time to recovery is defined as the first timepoint when total amplitude returns to at least 85% of the baseline value (the recovery is considered to be reached for all the visits occurring after the time to recovery).
- Duration of response defined as time between time to onset and time to recovery of CMAP total amplitude
- Maximal inhibition (maximal effect) reached defined as the maximal measured inhibition of CMAP amplitude of stimulated EDB
- Time to maximal effect on the CMAP total amplitude of stimulated EDB defined on an individual basis as the time between baseline and the timepoint of maximal inhibition of CMAP amplitude of stimulated EDB.

All the endpoints defined above will be analysed descriptively only and listed.

Skin temperature and stimulation intensity will be also collected for quality control, described and listed.

5.7.5 *Analysis of Exploratory Endpoints*

The following exploratory endpoint will be analysed using the same MMRM model used for the primary analysis:

- CMAP total amplitude at all timepoints, measured as percentage relative to baseline (%), calculated as [value at the timepoint (mean of the three measurements)/ baseline value (means of the six measurements)]*100.

Graphical representation of adjusted means (SE) coming from the MMRM model will be performed over time by study intervention group.

Latency of M-wave at all timepoints will be analysed descriptively only and listed.

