9 STATISTICAL CONSIDERATIONS

9.1 Statistical Hypotheses

The primary endpoint, CMAP total amplitude at Week 28, measured as relative change from Baseline (%), will be analysed using a mixed-effects model for repeated measures (MMRM), $\delta_{db} = \mu_{dysport} - \mu_{botox}$ and $\delta_{dx} = \mu_{dysport} - \mu_{xeomin}$ are the contrasts (i.e. mixed model Wald tests) of the Dysport versus Botox versus Xeomin comparisons in the primary endpoint at Week 28 of the study. Two elemental null hypotheses will be investigated,

$$H_{0,db,1} : \delta_{db} = 0 \text{ and}$$

$$H_{0,dx,1} : \delta_{dx} = 0.$$

These null hypotheses of no difference between the respective treatment arms in the primary endpoint will be tested against the respective two-sided alternative hypotheses

$$H_{A,db,1} : \delta_{db} \neq 0 \text{ and}$$

$$H_{A,dx,1} : \delta_{dx} \neq 0$$

at a 5% significance level ($\alpha = 0.05$) using a MMRM model and mixed model Wald tests of the respective contrast the Dysport versus Botox versus Xeomin comparisons in the primary endpoint at Week 28 of the study.

To control for the family-wise type I error rate at the two-sided level $\alpha = 0.05$, a Hochberg procedure [Dmitrienko and D'Agostino 2013] will be applied to investigate the two null hypotheses $H_{0,db,1}$ and $H_{0,dx,1}$. The testing procedure uses the following decision rules for the two p-values p_{db} and p_{dx} :

- Both null hypotheses are rejected if $\max(p_{db}, p_{dx}) \leq \alpha$
- Only the null hypothesis corresponding to the smaller p-value $\min(p_{db}, p_{dx})$ is rejected if $\min(p_{db}, p_{dx}) \leq \alpha/2$ and $\max(p_{db}, p_{dx}) > \alpha$.

If both null hypotheses of the primary endpoint are rejected, then the same Hochberg procedure will be applied sequentially to the two respective null hypotheses comparing Dysport with Botox and with Xeomin for secondary endpoints in the following order:

1. CMAP total amplitude at Week 40 post-injection
2. Incidence of recovery of CMAP total amplitude at Week 28 post-injection
3. Incidence of recovery of CMAP total amplitude at Week 40 post-injection

The two null hypotheses of secondary endpoint k , $k = 2, 3$ are tested with a Hochberg procedure, when both null hypotheses of endpoint $k-1$ are rejected.

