5.7.1.1 Significance Testing and Estimations

All statistical tests will be two-sided at the 5% level of significance unless otherwise specified. Confidence Intervals (CI) will be 95%, unless otherwise specified in the description of the analyses.

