5.7.1.3 Statistical/analytical issues

Adjustments for Covariates

Not applicable.

Interim Analyses and Data Monitoring

Not applicable.

Multicentre Studies

This is a single-centre study.

Multiple Testing

To control for the family-wise type I error rate at the two-sided level $\alpha = 0.05$, a Hochberg -procedure will be applied to investigate the two null hypotheses $H_{0,db} : \delta_{db} = 0$ and $H_{0,dx} : \delta_{dx} = 0$. The testing procedure uses the following decision rules for the two p-values p_{db} and p_{dx} :

- Both null hypotheses are rejected if $\max(p_{db}, p_{dx}) \leq \alpha$
- Only the null hypothesis corresponding to the smaller p-value $\min(p_{db}, p_{dx})$ is rejected if $\min(p_{db}, p_{dx}) \leq \alpha/2$ and $\max(p_{db}, p_{dx}) > \alpha$.

If both null hypotheses of the primary endpoint are rejected, then the same Hochberg procedure will be applied sequentially to the two respective null hypotheses comparing Dysport with Botox and with Xeomin for secondary endpoints in the following order:

4. CMAP total amplitude at Week 40 post-injection
5. Incidence of recovery of CMAP total amplitude at Week 28 post-injection
6. Incidence of recovery of CMAP total amplitude at Week 40 post-injection

The two null hypotheses of secondary endpoint k , $k = 2, 3$ are tested with a Hochberg procedure, when both null hypotheses of endpoint $k-1$ are rejected.

Convergence of the MMRM Model

If the default Newton-Raphson algorithm used by statistical analysis software PROC MIXED fails to converge, the Fisher scoring algorithm up to iteration 2 will be used (via the SCORING=2 option of the PROC MIXED statement) to obtain the initial values of covariance parameters [Mallinckrodt 2008]. If this alternative also fails to converge, then in addition the no-diagonal factor analytic structure (via the TYPE=FA0(T) option of the REPEATED statement, where T is the number of post baseline measurement timepoints incorporated in the MMRM analysis) will be used, which effectively performs the Cholesky decomposition of the covariance matrix and is numerically more stable.

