5.7.3 Analysis of Key Secondary Pharmacodynamic Endpoints

5.7.3.1 Endpoint, Treatment Effect and Estimand Definition

To assess the secondary objectives, the key secondary endpoints and estimands have the following key attributes:

- Population of interest: healthy adult male participants as defined by the listed inclusion/exclusion criteria in Section 5.1 and 5.2 of the protocol.
- Secondary endpoint of interest:
 - CMAP total amplitude at Week 40, measured as percentage relative to baseline (%), calculated as [value at Week 40 (mean of the three measurements)/baseline value (means of the six measurements)]*100
 - Incidence at Week 28 of recovery of CMAP total amplitude
 - Incidence of recovery of CMAP total amplitude at Week 40

The recovery is considered to be reached for all the visits occurring after the time to recovery, i.e. the first visit for which CMAP total amplitude return to at least 85% of the baseline value.

- ICEs are the following:
 - b) Study discontinuation
 - b1) PDs with potential impact on relevant CMAP total amplitude assessments (i.e. participant received the wrong study intervention and time window violation at the corresponding time point ($> +/- 2$ weeks)),
 - b2) PDs with no expected impact on relevant CMAP assessments (e.g. other time window violations, PDs related to covid-19)
- Treatment regimen: Dysport, Botox or Xeomin will be administered as described in Section 6 of the protocol and potential intake of permitted concomitant medications (for a list see Section 6.8 of the protocol).
- For ICEs (a) and (b1) a hypothetical strategy will be used, the treatment difference which would have been measured if the ICE would not have happened is of interest and will be assessed taking into account the long term pharmacodynamic effect of the investigated compounds. This implies that assessments after the occurrence of a major protocol deviation interfering with CMAP total amplitude will be ignored for the analysis. For CMAP total amplitude at Week 40, no imputation will be done (MMRM analysis). For the incidence of recovery, it will be considered as "No recovery" if the next available percentage CMAP relative to baseline (%) is inferior to 85% and will be imputed to the worst scenario "Recovery" if not or in case of no available CMAP after this ICE.

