b. Exact (Clopper-Pearson) 95% confidence intervals for proportion

To obtain the exact (Clopper-Pearson) 95% CI for proportion of participants with recovery in each of the treatment arms, the following SAS code will be used:

CCI

c. Exact unconditional 95% confidence interval for the risk differences and Fisher's Exact Test

To obtain the exact unconditional 95% CI for the risk differences as well as the Fisher's Exact Test (right-sided, significance level 2.5%), the following SAS code will be used:

CCI

Where AVAL is recovery of CMAP amplitude, AVISIT is Week 28 or Week 40. Same model will be performed with TRTP in ("Dysport" "Xeomin").

CCI

A5. PCSA criteria for vital signs parameters

PCSA criteria for vital signs parameters are defined as follow:

Parameter	PCSA criteria
Systolic Blood Pressure	≤ 90 mmHg and change from baseline ≤ -20 mmHg ≥ 180 mmHg and change from baseline ≥ 20 mmHg
Diastolic Blood Pressure	≤ 50 mmHg and change from baseline ≤ -15 mmHg ≥ 105 mmHg and change from baseline ≥ 15 mmHg
Heart Rate	≤ 50 bpm and change from baseline ≤ -15 bpm ≥ 120 bpm and change from baseline ≥ 15 bpm
Weight	$\leq -5\%$ change from baseline $\geq 5\%$ change from baseline

A6. Listings conventions

Any listings will contain at least the following data: participant identifier, age and gender. When dates are presented, the associated study days should be included. They should be sorted by study intervention group then participant identifier.

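### Does a one-sided 2.5% Fisher test inside a Hochberg rule written for two-sided alpha = 0.05 leave the recovery endpoints without a clear cut-off?

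*SAP*

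**What the plan says.** Protocol 9.4.3.1 and SAP 5.7.3.2.2 give the same test for recovery at Weeks 28 and 40: a Fisher's "Exact Test (one-sided, significance level 2.5%) will be used for testing each of the comparisons of Dysport to Botox or Xeomin respectively", placed within the multiple testing procedure.

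That procedure (Protocol 9.1; SAP 2.1.2 and 5.7.1.3) opens with "To control for the family-wise type I error rate at the two-sided level" alpha = 0.05. Its rules are written in symbols: reject both nulls if the larger p-value is at most alpha; otherwise reject only the smaller if it is at most alpha/2. If both primary nulls fall, "then the same Hochberg procedure will be applied sequentially to the two respective null hypotheses comparing Dysport with Botox and with Xeomin" on the secondary endpoints, in the order Week 40 amplitude, Week 28 recovery, Week 40 recovery.

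Three other places bear on the reading:
- SAP 5.7.1.1 sets the default: "All statistical tests will be two-sided at the 5% level of significance unless otherwise specified".
- SAP 5.7.3.1 treats recovery as the unfavourable outcome. Where the next CMAP value does not show continued inhibition, or there is none, the result "will be imputed to the worst scenario", namely recovery.
- SAP Appendix A4.c describes the Fisher's "Exact Test (right-sided, significance level 2.5%), the following SAS code will be used". The code itself is redacted.

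**The concern.** A one-sided p-value and a two-sided alpha are on different scales. The procedure is carried over as the same procedure, and no sentence says that alpha becomes 0.025, that the second cut-off becomes 0.0125, or that one-sided p-values are doubled. The figure 2.5% could even be taken for the printed alpha/2. An analyst who compared one-sided p-values with 0.05 and 0.025 would sometimes reject where an analyst using 0.025 and 0.0125 would not.

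The formal alternatives in Protocol 9.1 and SAP 2.1.2 are two-sided and written for the primary endpoint only, so the direction of the one-sided test has to be inferred.

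Two of the three alpha-controlled key secondary endpoints use this rule, and Week 40 recovery is tested only if both Week 28 recovery nulls are rejected. If the cut-offs were really open, a pass or fail could be chosen once results were known.

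**Working it through.** **Inputs.** 15 per arm, 1:1:1 (Protocol 9.2, SAP 2.3); one-sided Fisher at 2.5% (SAP 5.7.3.2.2); cut-offs alpha and alpha/2 with two-sided alpha = 0.05 (SAP 5.7.1.3). The documents give no recovery rates, so those used in step 4 are assumptions.

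**The plan's own figure.** No power is stated for recovery. The primary power confirms the sample-size input: the noncentrality is 18 / (15 × √(2/15)) = 3.286 on 28 df, which gives 88.7% against the stated minimum of 88%. Simulation of both comparisons gives 81.3% against the stated minimum of 81%.

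**Step 1. Where the two readings part.** With d of 15 recovered on Dysport and c of 15 on a comparator, the one-sided p (fewer recoveries on Dysport) is Σ over k ≤ d of C(15,k)·C(15,d+c−k) / C(30,d+c).

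- 3 v 9: (2,277,275 + 315,315 + 20,475 + 455) / 86,493,225 = 0.0302.
- 3 v 10: (1,366,365 + 143,325 + 6,825 + 105) / 119,759,850 = 0.0127.
- 3 v 8: 0.0641.

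| Recovered (Dysport, Botox, Xeomin) | One-sided p | Literal 0.05/0.025 | Converted 0.025/0.0125 |
|---|---|---|---|
| 3, 9, 9 | 0.0302, 0.0302 | rejects both | rejects neither |
| 3, 10, 8 | 0.0127, 0.0641 | rejects Botox only | rejects neither |

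Of the 256 two-arm tables, ten have p in (0.025, 0.05] and seven in (0.0125, 0.025]. Only these can separate the readings.

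**Step 2. Does the text allow both readings?** In the first row, p = 0.0302 exceeds the stated one-sided level of 0.025, and the doubled value, 0.0604, exceeds the two-sided level of 0.05. Rejecting would breach both stated levels. In the second row, the doubled value is 0.0253 against alpha/2 = 0.025, so the two-sided rule would not reject either. Because the rule is symbolic, putting the endpoint's own level in for alpha gives 0.025 and 0.025/2 = 0.0125.

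**Step 3. Does the converted rule match the two-sided rule?** There are 1,496 three-arm outcomes in which Dysport has no more recoveries than either comparator. One-sided p against 0.025/0.0125 and two-sided Fisher p against 0.05/0.025 gave the same decision in all of them.

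**Step 4. Size if the literal reading were used.** Exact enumeration of three binomial arms:

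| Assumed recovery, Dysport v each comparator | Readings differ on at least one null | Power for both, literal | Power for both, converted |
|---|---|---|---|
| 20% v 60% | 0.23 | 0.43 | 0.28 |
| 10% v 50% | 0.19 | 0.53 | 0.38 |
| 30% v 80% | 0.19 | 0.70 | 0.54 |

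The largest family-wise error in a scan of rates was 1.79% (literal) and 0.90% (converted) with all arms equal, and 2.16% and 0.88% with one true null. All are below 2.5%, because Fisher's test is conservative at this size.

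**Step 5. Direction.** The primary objective is longer action of Dysport, and recovery is imputed as the worst case. Both point to p_D < p_B and p_D < p_X. Whether the right-sided label matches depends on row and column order, which the redacted code sets. That cannot be checked and is not evidence of an error.

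**The case for a change.** The strongest case for a change is that endpoints under formal alpha control should have their cut-offs written down. The number 0.0125 appears nowhere, 2.5% coincides with the printed alpha/2, and under the assumed rates the two readings would disagree in roughly one trial in five. The remedy would be a sentence or two, and SAP 2.6 already lists clarifications of that kind.

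The arithmetic stands, and so does the observation that the conversion and a formal alternative are unwritten in the visible text. The claim that the two readings are equally open does not stand. The one-in-five figure counts disagreement with a reading that the stated level rules out. It is also unconditional: it ignores that recovery is tested only after four earlier rejections, and it rests on recovery differences of 40 to 50 points that the documents do not supply. The worry about a choice made after unblinding is limited too, since SAP section 1 has the plan finalised before database lock and requires later departures to be reported.

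**Conclusion.** No change follows. The plan omits a unit conversion that its own stated level supplies: one-sided p-values go against 0.025 for both nulls and 0.0125 for the smaller alone, with fewer recoveries on Dysport as the alternative. Any analyst used to pairing one-sided 2.5% with two-sided 5% would do this, and would reach the two-sided Hochberg decision in all 1,496 outcomes where Dysport recovers no more often than either comparator.

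Even a slip to the literal cut-offs would not raise the family-wise error above one-sided 2.5% (largest found 2.16%, from a scan of rates and not a proof). The primary endpoint and Week 40 amplitude are untouched. These results assume 15 evaluable participants per arm; the power and disagreement figures also depend on assumed recovery rates.

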9.4.3 Analysis of Secondary Endpoints

9.4.3.1 Incidence of Recovery of CMAP Total Amplitude at Week 28 and Week 40

Recovery of CMAP total amplitude is defined as a return of total amplitude to at least 85% of the Baseline value. Incidence of recovery of CMAP total amplitude at Weeks 28 and 40 will be analysed for each of the two timepoints by estimating proportion of participants with recovery in each of the treatment arms, p_D in the Dysport arm, p_B in the Botox arm, p_X in the Xeomin arm, as well as the risk differences $p_D - p_B$ and $p_D - p_X$ with point estimates as well as according exact (Clopper-Pearson) 95% confidence intervals for p_D , p_B and p_X and exact unconditional 95% confidence interval for the risk differences.

A Fisher’s Exact Test (one-sided, significance level 2.5%) will be used for testing each of the comparisons of Dysport to Botox or Xeomin respectively in the framework of the multiple testing procedure described in Section 9.1.

9.4.3.2 CMAP Total Amplitude at Week 40

CMAP total amplitude at Week 40 will be analysed using the same MMRM model used for the primary analysis.

9.4.3.3 *Time to Onset of Action*

Time to onset of action will be analysed descriptively. Onset of action is defined as the first timepoint where EDB CMAP total amplitude is 85% or lower than the Baseline value.

9.4.3.4 *Duration of Response*

Duration of response will be analysed descriptively. Duration of response is defined as the time between onset of action and recovery of CMAP total amplitude (where recovery is defined as return to at least 85% of the Baseline value).

9.4.3.5 *Maximal Effect*

Maximal Effect for each participant is defined as the maximal measured inhibition of CMAP amplitude of stimulated EDB. Maximal Effect will be analysed descriptively.

9.4.3.6 *Time to Maximal Effect*

Time to maximal effect will be analysed descriptively. Time to maximal effect is defined on an individual basis as the time between Baseline and the timepoint of maximal inhibition of CMAP amplitude of stimulated EDB.

9.4.4 *Safety Analyses*

All safety analyses will be made on the Safety Population.

Summary statistics will be presented by study intervention group and overall for vital signs, physical examination, at each assessment.

Adverse Events

All AEs will be coded according to the Medical Dictionary for Regulatory Activities (MedDRA) (last applicable version) and will be classified by MedDRA preferred term and system organ class.

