2.1.2 Statistical Hypotheses

The primary endpoint, CMAP total amplitude at Week 28, measured as percentage relative to baseline (%), will be analysed using a Mixed-effects Model for Repeated Measures (MMRM), $\delta_{db} = \mu_{dysport} - \mu_{botox}$ and $\delta_{dx} = \mu_{dysport} - \mu_{xeomin}$ are the contrasts (i.e. mixed model Wald tests) of the Dysport versus Botox versus Xeomin comparisons in the primary endpoint at Week 28 of the study. Two elemental null hypotheses will be investigated,

$$H_{0,db,1} : \delta_{db} = 0 \text{ and}$$

$$H_{0,dx,1} : \delta_{dx} = 0.$$

These null hypotheses of no difference between the respective treatment arms in the primary endpoint will be tested against the respective two-sided alternative hypotheses

$$H_{A,db,1} : \delta_{db} \neq 0 \text{ and}$$

$$H_{A,dx,1} : \delta_{dx} \neq 0$$

at a 5% significance level ($\alpha = 0.05$) using a MMRM model and mixed model Wald tests of the respective contrast the Dysport versus Botox versus Xeomin comparisons in the primary endpoint at Week 28 of the study.

To control for the family-wise type I error rate at the two-sided level $\alpha = 0.05$, a Hochberg procedure [Dmitrienko and D'Agostino 2013] will be applied to investigate the two null hypotheses $H_{0,db,1}$ and $H_{0,dx,1}$. The testing procedure uses the following decision rules for the two p-values p_{db} and p_{dx} :

- Both null hypotheses are rejected if $\max(p_{db}, p_{dx}) \leq \alpha$
- Only the null hypothesis corresponding to the smaller p-value $\min(p_{db}, p_{dx})$ is rejected if $\min(p_{db}, p_{dx}) \leq \alpha/2$ and $\max(p_{db}, p_{dx}) > \alpha$.

If both null hypotheses of the primary endpoint are rejected, then the same Hochberg procedure will be applied sequentially to the two respective null hypotheses comparing Dysport with Botox and with Xeomin for secondary endpoints in the following order:

- CMAP total amplitude at Week 40 post-injection
- Incidence of recovery of CMAP total amplitude at Week 28 post-injection
- Incidence of recovery of CMAP total amplitude at Week 40 post-injection

The two null hypotheses of secondary endpoint k, k =2, 3 are tested with a Hochberg procedure, when both null hypotheses of endpoint k-1 are rejected.

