2.6 Change from Statistical Section of the Protocol

No change from statistical section of the protocol has been done, only clarifications have been made:

- The wording of the primary endpoint has been updated from "CMAP total amplitude relative change from Baseline (%)" to "CMAP percentage relative to baseline (%)".
- The following secondary endpoints: CMAP total amplitude at Week 40, incidence at Week 28 of recovery of CMAP total amplitude and incidence of recovery of CMAP total amplitude at Week 40, for which the alpha risk is controlled, are considered as key secondary endpoints.
- The definition of the time to onset of action has been updated from "Time to onset of action is defined as the first timepoint where EDB CMAP total amplitude is 85% or lower than the Baseline value" to "time to onset of action is defined as first timepoint where EBD CMAP total amplitude is less or equal to 85% of the baseline value".

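### Optional improvement, not an error: the one-sided 2.5% Fisher test for recovery uses only 0.88% of its level at 15 v 15; Boschloo's test keeps every Fisher rejection and stays within 2.5%

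*SAP*

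**What the plan says.** SAP 5.7.3.2.2 tests recovery incidence at Weeks 28 and 40 with Fisher's "Exact Test (one-sided, significance level 2.5%) will be used for testing each of the comparisons of Dysport to Botox or Xeomin respectively". Protocol 9.4.3.1 plans the same test at the same level, "respectively in the framework of the multiple testing procedure described in Section 9.1". SAP Appendix A4.c repeats it as Fisher's "Exact Test (right-sided, significance level 2.5%), the following SAS code will be used"; the code itself is redacted.

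The multiplicity rule is written on the two-sided scale. SAP 2.1.2 opens it with "To control for the family-wise type I error rate at the two-sided level" 0.05 and prints the Hochberg cut-offs as alpha and alpha/2. SAP 5.7.1.3 adds that, once both primary nulls are rejected, "then the same Hochberg procedure will be applied sequentially to the two respective null hypotheses comparing Dysport with Botox and with Xeomin" for the key secondary endpoints. The order is Week 40 amplitude, Week 28 recovery, Week 40 recovery. SAP 5.7.1.1 sets the default: "All statistical tests will be two-sided at the 5% level of significance unless otherwise specified".

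Recovery is the unfavourable outcome for Dysport. In SAP 5.7.3.1 a missing status that cannot be called no recovery "will be imputed to the worst scenario", namely recovery.

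There are 15 participants per arm (SAP 2.3) and dropouts are not replaced (SAP 2.4). The PD set needs a baseline and at least one later CMAP recording (SAP 4), so arms may end slightly below 15 and unequal. Neither document states an attained size or a power for the recovery tests.

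**The concern.** Fisher's test conditions on the total number of recoveries. With 15 per arm, few p-values are then possible, so the test can fall well short of its nominal 2.5%. Recovery at each week is an alpha-controlled key secondary endpoint, and both Week 28 nulls must fall before Week 40 recovery is tested. Unused level therefore costs power twice, in each comparison and in passing the gate.

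A smaller point belongs with it. The Hochberg cut-offs are printed for two-sided alpha = 0.05, while the recovery test is one-sided at 2.5%. The natural translation is 0.025 and 0.0125 for one-sided p-values, but this is not written. Nor does the body text state the direction of the alternative.

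**Working it through.** **The plan's own power figure.** It concerns Week 28 amplitude only. With difference 18, SD 15 and 15 per arm, the noncentrality is 18 / (15 × √(2/15)) = 3.286 on 28 df. The two-sided 5% t-test then has power 88.7%, which agrees with the stated 88% or more. Nothing comparable is stated for recovery.

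**Method.** Let x_D of n_D Dysport and x_C of n_C comparator participants recover; the alternative is p_D < p_C.

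- Fisher p = P(X ≤ x_D), with X hypergeometric given x_D + x_C recoveries.
- Boschloo p = maximum over a common rate π of P_π(Fisher p ≤ observed Fisher p).
- Size = maximum over π of Σ Bin(x_D; n_D, π) × Bin(x_C; n_C, π), summed over the rejected tables.

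All tables were enumerated for 13 to 15 per arm. That range is an assumption, because the documents give no dropout rate.

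**Maximum one-sided size per comparison (%), by cut-off for the one-sided p-value**

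| Arms | Fisher, 0.025 | Boschloo, 0.025 | Boschloo, 0.0125 | Fisher, 0.05 |
|---|---|---|---|---|
| 15 v 15 | 0.88 | 2.16 | 1.17 | 2.16 |
| 15 v 14 | 1.24 | 2.46 | 1.24 | 3.14 |
| 15 v 13 | 0.94 | 2.12 | 1.21 | 2.12 |
| 14 v 14 | 1.07 | 2.08 | 1.07 | 2.08 |
| 14 v 13 | 1.07 | 1.89 | 1.21 | 2.68 |
| 13 v 13 | 1.45 | 2.43 | 0.96 | 2.43 |

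At 15 v 15 and 0.025, Fisher rejects 51 tables and Boschloo 61. At 0.0125 the counts are 44 and 53. No Fisher rejection is lost at any of these sizes. One added table is 3/15 v 9/15 (Fisher 0.0302, Boschloo 0.0150).

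**Hochberg error over both comparisons**, summed exactly over the shared Dysport arm. Under the global null all three rates are equal. Under a partial null one comparator truly differs, and the error is a false rejection for the other.

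| Test and cut-offs | Global null, 15/15/15 | Global null, largest over 13 to 15 | Partial null, largest |
|---|---|---|---|
| Boschloo, 0.025/0.0125 | 2.29% | 2.41% | 2.46% (15 v 14) |
| Fisher, 0.05/0.025 | 1.79% | 2.75% (13/13/13) | 3.14% (15 v 14) |
| Boschloo, 0.05/0.025 | 4.32% | 4.69% | 4.99% (14 v 13) |

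At exactly 15 per arm, the partial-null error with Fisher at 0.05/0.025 is 2.16%. With one-sided Fisher p-values set against the printed numbers, the error thus passes 2.5% only if arms fall below 15. It does so at 13/13/13 under the global null, and at 15 v 14 or 14 v 13 under a partial null.

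**Illustrative power at 15 per arm, cut-off 0.025.** The rates are assumed. Both comparisons are rejected with probability Σ Bin(x_D; 15, p_D) × [P(reject | x_D)]².

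| Dysport v comparator | One comparison, Fisher → Boschloo | Both, Fisher → Boschloo |
|---|---|---|
| 20% v 60% | 44.7% → 59.9% | 27.9% → 43.0% |
| 30% v 70% | 43.4% → 59.0% | 27.1% → 42.9% |
| 20% v 70% | 68.0% → 80.7% | 52.7% → 69.2% |

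These figures take the recovery test as reached. A simulation put the four amplitude rejections first, using t-tests in place of the MMRM. It assumed an 18-point difference at Week 28, SD 15, between-visit correlation 0.5 to 0.9 and group midpoints of 75% to 95% of baseline. The gain in rejecting both Week 28 recovery nulls was then 12 to 15 points if the Week 40 difference stays at 18, 9 to 12 if it is 15, and 6 to 7 if it is 12.

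**The case against.** The strongest reply is that this is a matter of preference. Fisher's test is familiar, valid and prespecified alike in both documents. The plan sets no power target for recovery, which comes third and fourth in a fixed sequence. That stands, and it is why the point is optional.

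The power figures can also be attacked. The rates are assumed, and the calculation ignores two rules in SAP 5.7.3.1: recovery is carried forward from the first visit that reaches 85%, and some missing statuses are imputed as recovery. That stands too, so the figures illustrate and do not predict. The size comparison needs no assumed rates.

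On scale and direction, much is already there. The sentence that names the test says one-sided 2.5%, and SAP 5.7.1.1 allows exceptions to its two-sided default. The objective of longer Dysport action, with recovery as the bad outcome, implies p_D < p_C. A reader might go further and infer that the plan contradicts itself, that its error rate is inflated, or that A4.c tests the wrong tail. The documents support none of these. The stated 2.5% level speaks against a 0.05 cut-off for one-sided p-values, and which tail is right-sided depends on a table orientation in code that is redacted.

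**Conclusion.** The planned test controls type I error; nothing needs correcting for validity. At 15 v 15 it uses about a third of its nominal level (0.88% of 2.5%). Boschloo's test dominates it at every size of 13 to 15 per arm and keeps the Hochberg error within 2.5%, provided one-sided p-values meet 0.025 and 0.0125. The 2.41% figure is the global-null maximum only; the largest value to quote is 2.46%.

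It might be inferred that the trial gains some 15 percentage points of power. That does not follow, because the gain depends on unknown recovery rates and on first rejecting four amplitude nulls. Nor can the scale be left unwritten on the ground that Fisher's conservatism absorbs any misreading; that fails once arms drop below 15.

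The sizes assume independent binomial counts in each arm. This is a modest, optional improvement.

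**What to change.** In SAP 5.7.3.2.2, name Boschloo's exact unconditional test in place of Fisher's. State that one-sided p-values for p_D < p_B and p_D < p_X enter the Hochberg rule against 0.025 (both rejected) and 0.0125 (smaller one only). Give the table orientation that makes A4.c's right-sided tail match. Name the ordering explicitly, because not every unconditional test contains Fisher's rejections: one ordered on the raw risk difference gives 0.0494 for 0/15 v 5/15, where Fisher gives 0.0211.

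The cost is a few lines of text and a short code change before database lock; each comparison has at most 16 × 16 = 256 tables. The test is less familiar and less conservative, and it need not agree exactly with the planned unconditional interval for the risk difference. It also departs from the Protocol, so SAP 2.6, which now says "No change from statistical section of the protocol has been done, only clarifications have been made", must record it as a change.

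If Fisher is kept, add only the sentence on scale and direction.
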